6.2.2.6. Severity Increase and Potentiation for Reactogenicity Across Doses

This derivation will be applied to each local reaction and each systemic event (including fever).

These endpoints will be derived as following:

Table 7. Derived Variables for Increasing Severity and Potentiation

Variable	Yes (1)	No (0)	Missing
Increasing Severity (days 1-7)	If the maximum severity is more severe in any following dose(s) compared with the previous dose(s)	If the maximum severity for the later dose(s) is at most the same severity as the previous dose(s)	If all data for the reaction is missing for all days 1-7 after dose 1, dose 2 and dose 3 or only 1 dose was received.
Potentiation (days 1-7)	If the maximum severity is more severe following dose 2 than dose 1, AND more severe following dose 3 than dose 2	If the maximum severity post dose 2 is at most the same severity as post dose 1, OR the maximum severity post dose 3 is at most the same severity as post dose 2	If all data for the reaction is missing for all days 1-7 after any dose, or less than 3 doses were received.

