## 5.5. Administration

Standard vaccination practices must be observed and vaccine must not be injected into blood vessels. Appropriate medication and other supportive measures for management of an acute hypersensitivity reaction should be available in accordance with local guidelines for standard immunization practices.

Administration of investigational products should be performed by an appropriately qualified, Good Clinical Practice (GCP)-trained, and vaccine-experienced member of the study staff (eg, physician, nurse, physician's assistant, practitioner, pharmacist, or medical assistant) as allowed by local, state, and institutional guidance. In this observer-blinded study, the study staff dispensing and administering the vaccine will be unblinded, but all other study personnel, including the principal investigator and the sponsor, will be blinded.

Investigational product administration details (ie, date of administration, container number, volume, route, and site of administration, administration errors) will be recorded on the CRF.

During the study, subjects in Group 1 will be administered bivalent rLP2086 by intramuscular injection at Months 0, 2, and 6 into the upper deltoid muscle of the arm.

Subjects in Group 2 will be administered HAV vaccine/saline/HAV vaccine at Months 0, 2, and 6 into the upper deltoid muscle of the arm.

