2.1. Study Design

This is a Phase 2, randomized, controlled, observer-blinded, multicenter study in which approximately 400 healthy subjects will be randomized in a 3:1 ratio to receive either bivalent rLP2086 at Months 0, 2, and 6, or HAV vaccine at Months 0 and 6 and saline at Month 2. Subjects will be stratified equally into 2 age groups: ≥24 months to <4 years or ≥4 years to <10 years.

Table 1. Study Design

	Vaccination (Vax) 1	Post-Vax 1 Follow-up	Vax 2	Post-Vax 2 Blood Draw	Vax 3	Post-Vax 3 Blood Draw	Month 12 Follow-up and Blood Draw
Visit number	1	2	3	4	5	6	7
Approx - month	0	1	2	3	6	7	12
Group 1 (300)	Bivalent rLP2086		Bivalent rLP2086		Bivalent rLP2086		

Table 1. Study Design

	Vaccination (Vax) 1	Post-Vax 1 Follow-up	Vax 2	Post-Vax 2 Blood Draw	Vax 3	Post-Vax 3 Blood Draw	Month 12 Follow-up and Blood Draw
Group 2 (100)	HAV vaccine		Saline		HAV vaccine		
Blood draw	5-10 mL			5-10 mL		5-10 mL	5-10 mL

Abbreviations: HAV = hepatitis A virus; Vax = vaccination.

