5.3. Safety Analysis Set

All subjects who received at least 1 dose of the investigational product (rLP2086, HAV vaccine or saline) and with safety data available will be included in the safety population. The safety population will be used for all of the safety analyses. The following separate safety populations will be defined: vaccination 1, vaccination 2, vaccination 3, and follow-up.

1. Vaccination 1 Safety Population: This population will include all subjects who received the first dose of the investigational products (rLP2086 or HAV vaccine) at visit 1.
2. Vaccination 2 Safety Population: This population will include all subjects who received the investigational product (rLP2086 or saline) at visit 3.
3. Vaccination 3 Safety Population: This population will include all subjects who received the investigational product (rLP2086 or HAV vaccine) at visit 5.

4. Follow-up Safety Population: This population will include all subjects who received at least 1 dose of investigational product (rLP2086, HAV vaccine or Saline) and for whom safety information is available from after visit 6 to visit 7, or from the time of subject withdrawal to visit 7.

In the safety analysis set, subjects will be analyzed according to the investigational product received.

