8.2.5. Analysis of Safety Data

8.2.5.1. Reactogenicity Data

The presence of each local reaction, each systemic event, fever, use of antipyretic medication at each specific day (day 1, day 2,day 7) will be summarized with number and proportion of subjects reporting such event, for each vaccination. The presence and maximum severity of each local reaction, systemic events, and fever at 'any day 1-7' will be summarized with number and proportion of subjects reporting such event, by each vaccination as well as 'after any vaccination'. The summaries will include 95% Clopper-Pearson's CI.

Proportion differences (Group 1-Group 2), associated 95% CIs and p-values will only be provided, by each vaccination and after any vaccination for the following endpoints:

- any local reactions (overall and by type of event) and any severe local reactions (only overall)
- any systemic events (overall and by type of event) and severe systemic events (only overall)
- any use of anti-pyretics
- any fever and also any temperature above or equal to 39.0-39.9 and 40 degrees centigrade.

Also, the increasing severity and potentiation of local and systemic reactions across all 3 vaccinations will be summarized with number and proportion of subjects with such characteristics, along with 95% exact CI.

The aggregated variable for antipyretic use and fever will also be summarized with number and percentage, along with 95% exact CI (multinomial data),^a for each vaccination.

For local reactions and systemic events, including fever and use of antipyretic medication, the maximum duration of the event will be summarized for each vaccination. The number of unknown durations will also be summarized. The onset day for each local reaction and systemic event will also be summarized.

All of these summaries will be summarized according to the vaccine received. The safety population at each corresponding dose will be used for the analyses for each vaccination. The data summaries will be descriptively presented by group.

^a Goodman's Bonferroni based procedure, with Blyth-Still-Casella intervals as the basis for the Bonferroni procedure (StatXact 9 User Manual)

A listing will be provided for all of the severe reactogenicity data.

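### SAP Table 7 scores increasing severity and potentiation by dose number alone, but control dose 2 is saline, so the control column does not describe repeat-dose worsening of one product

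*SAP*

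**What the plan says.** SAP 6.2.2.6 (Table 7) defines two derived variables for each local reaction and each systemic event, including fever. Potentiation is Yes "If the maximum severity is more severe following dose 2 than dose 1, AND more severe following dose 3 than dose 2". Increasing severity is Yes "If the maximum severity is more severe in any following dose(s) compared with the previous dose(s". Neither row refers to product or group.

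The two rows treat missing data differently. Potentiation is Missing "If all data for the reaction is missing for all days 1-7 after any dose, or less than 3 doses were received". Increasing severity is Missing "If all data for the reaction is missing for all days 1-7 after dose 1, dose 2 and dose 3 or only 1 dose" (the last part meaning that the child got a single dose).

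SAP 8.2.5.1 states that "the increasing severity and potentiation of local and systemic reactions across all 3 vaccinations will be summarized" with exact 95% confidence intervals, and that the reactogenicity summaries are shown descriptively by group. The same section restricts between-group differences, their intervals and p-values to a list that contains neither variable.

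The control regimen is stated openly. SAP 2.1 gives it as "HAV vaccine at Months 0 and 6 and saline at Month 2", and Protocol 5.5 says "Subjects in Group 2 will be administered HAV vaccine/saline/HAV vaccine at Months 0, 2, and 6". Protocol 3.1 explains that the saline is there to keep the blind. SAP 5.3 recognises the difference in product when it defines the Vaccination 2 Safety Population: "This population will include all subjects who received the investigational product (rLP2086 or saline) at visit 3". Nothing in the SAP carries that distinction into Table 7, limits the two variables to Group 1, or adds a caveat.

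**The concern.** The two variables are meant to show whether reactions worsen as a child receives more doses. In Group 1 all three doses are bivalent rLP2086, so the rule does that. In Group 2 the same rule crosses products twice.

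The primary safety objective (Protocol 2.1.2) compares rLP2086 with the control, so a reader of a by-group table will naturally set the columns side by side and take the control percentage as what repeat vaccination does anyway. The Group 2 rule does not measure that. A low control potentiation rate could reflect only that saline hurts less than vaccine. A high control increasing-severity rate could reflect only that the second HAV dose hurts more than saline.

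**Working it through.** **Which comparisons the rule makes.** Write a, b, c for maximum severity (0 none to 3 severe) after Visits 1, 3 and 5.

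| | Group 1 | Group 2 |
|---|---|---|
| b against a | rLP2086 dose 2 vs dose 1 | saline vs HAV dose 1 |
| c against b | rLP2086 dose 3 vs dose 2 | HAV dose 2 vs saline |
| c against a | dose 3 vs dose 1 | HAV dose 2 vs HAV dose 1 |

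Potentiation needs a < b < c. In Group 2 this requires saline to react worse than the first HAV dose. If saline never produces the event (b = 0), it is impossible. Only the last row compares one product with itself in Group 2, and neither variable isolates it.

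**Inputs.** The documents state no reaction rates, no within-child correlation and no figure for either variable, so there is nothing to reproduce. Everything below is assumed: three severity profiles (none/mild/moderate/severe, %), no true dose effect, and at first independent doses and inert saline.

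**Potentiation.** For one product given three times, P(a < b < c) is the sum of p_i·p_j·p_k over i < j < k.
- 55/33/11/1: 0.01997 + 0.00182 + 0.00061 + 0.00036 = 2.3%
- 40/35/22/3: 0.03080 + 0.00420 + 0.00264 + 0.00231 = 4.0%
- 20/40/33/7: 0.02640 + 0.00560 + 0.00462 + 0.00924 = 4.6%

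Vaccine/saline/vaccine with inert saline gives 0 each time, so the gap is 2.3 to 4.6 points.

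With saline that does react (doses still independent; vaccine split 60/30/10 and saline 85/13/2 among reactors), the pairs are:

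| Any reaction, vaccine / saline | Same product ×3 | Vaccine/saline/vaccine |
|---|---|---|
| 30% / 10% | 1.8% | 0.8% |
| 50% / 20% | 3.6% | 1.8% |
| 80% / 30% | 4.4% | 1.8% |
| 80% / 10% | 4.4% | 0.6% |

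The control sequence yields about 0.14 to 0.50 times the same-product rate. Within-child correlation shrinks both: for 55/33/11/1 at correlation 0.8, the same-product rate is 0.3% and the control-sequence rate 0 to 0.2%.

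**Increasing severity, read as worse than any earlier dose.** For one product with independent doses, P(Yes) = 1 − P(a ≥ b ≥ c) = 1 − (1 + 3·Σp² + 2·Σp³)/6. With inert saline in the middle, P(Yes) = P(c > 0), whatever happened after Visit 1.
- 55/33/11/1: 1 − (1 + 3×0.4236 + 2×0.2036)/6 = 55%, against 45% for the control sequence
- 40/35/22/3: 1 − (1 + 3×0.3318 + 2×0.1176)/6 = 63%, against 60%
- 20/40/33/7: 1 − (1 + 3×0.3138 + 2×0.1083)/6 = 64%, against 80%

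The sign changes with the profile. It also changes with correlation: for 55/33/11/1 at 0.8, the same-product rate falls to 30% while the inert-saline rate stays at 45%. In the limiting case where a child's two HAV reactions are identical, the four vaccine/saline settings in the table above score 35% to 78% of controls Yes, against 0% for one product given three times.

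**Increasing severity, read as worse than all earlier doses.** For 55/33/11/1 over correlations 0 to 0.8, the control sequence gives 15% to 38% and the same-product series 24% to 46%. The control sequence is lower in each matched scenario.

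**The phrase for previous doses.** Moving between the two readings changes the same-product rate by 7 to 15 points across the three profiles and correlations 0 to 0.8. This wording question touches Group 1 too.

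**Missing rule.** A child with two or three doses but diary data after only one has nothing to compare, yet the increasing-severity row does not make that child Missing. If a fraction m of children lack all diary data after a given dose, independently across doses, the share with data after exactly one of three doses is 3(1 − m)m².
- m = 1%: 0.03%, or 0.1 of 400
- m = 2%: 0.12%, or 0.5 of 400
- m = 5%: 0.71%, or 2.9 of 400

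**The case against.** The best reply is that the SAP invites no misreading. It never calls the control column a background rate, plans no between-group difference or p-value for either variable, and does not list them among the primary safety endpoints in SAP 6.2.1. Each column correctly describes the regimen that group received. SAP 8.2.5.1 also tabulates maximum severity after each vaccination by group, so readers will see the HAV, saline and HAV visits separately. All of this stands and keeps the point minor. What remains is that the within-child pairing of the two HAV doses appears nowhere, and the variables that look as if they supply it do not.

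Two further replies also stand. First, the zero result is conditional. For fever, vomiting, diarrhea or fatigue, it would require that no child has the event from any cause in the 7 days after saline, which the documents do not support. The profiles above are illustrations in the style of injection-site pain; no systemic event was modelled. Second, SAP section 2 places programming rules in a separate document, which may already settle the previous-dose wording and the Missing rule. SAP 7.2 excludes children whose data are missing on every day of the interval, but does not say how that works for a variable spanning three intervals.

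**Conclusion.** The point holds as a minor correction to a descriptive table. In Group 2, Table 7 does not measure repeat-dose worsening of one product. That follows from the definitions and the regimen, with no assumed rates.

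Size and direction do rest on assumptions. The potentiation gap is about 2 to 5 points with independent doses and inert saline, and was smaller in the scenarios where saline reacts or a child's reactions are correlated. Increasing severity may be higher or lower in controls.

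A reader might infer more than this, in three ways:
- That the plan sets up a biased safety comparison against rLP2086. It does not: no between-group statistic is planned for these variables, and the saline issue does not alter any Group 1 figure.
- That control potentiation must be zero. That is so only for an event that never follows saline.
- That the gap is at most about 2 points and could not be seen, or that control increasing severity is lower at low correlation. Those statements hold only for the 55/33/11/1 profile. The other profiles give gaps of 4.0 and 4.6 points, above the exact upper 95% limit for 0 of 100 controls (1 − 0.025^(1/100) = 3.6%), and 20/40/33/7 reverses the direction.

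The Missing-rule gap is real but concerns very few children. The previous-dose wording needs clarification only.

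**What to change.** - Add one variable to the by-group table: maximum severity after Visit 5 greater than after Visit 1, Missing if diary data are absent after either. It compares the third with the first rLP2086 dose in Group 1 and the second with the first HAV dose in Group 2. Note beside it that dose number still differs between groups.
- Present the three-dose variables for Group 1 only, or footnote the Group 2 column as HAV/saline/HAV and not comparable.
- Align the increasing-severity Missing rule with the potentiation row to the extent that a child with diary data after only one dose is Missing.
- State whether the comparison is with any or with all earlier doses.

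The cost is one derived variable, revised wording in one row of Table 7, and a table shell or footnote. No new data are needed and no primary analysis changes.

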6.2.3. Safety Data Collected Through CRF

The CRF is designed to collect newly diagnosed chronic medical conditions and adverse events on 2 different pages. A medically-attended adverse event is defined as a non-serious adverse event that results in an evaluation at a medical facility. A newly diagnosed chronic medical condition is defined as a disease or condition not previously identified that is expected to be persistent or otherwise long-lasting in its effects.

The relationship between (S)AEs and the investigational products (rLP2086 vaccine, HAV/saline vaccine) will be characterized as related or not related as described in the protocol. The severity of AEs will be characterized as mild, moderate, and severe, as shown in the table below.

Table 8. Grading of AE Severity

Grade	
Mild	Does not interfere with subject’s usual function
Moderate	Interferes to some extent with subject’s usual function
Severe	Interferes significantly with subject’s usual function

Adverse events prior to first vaccination will be excluded from the AE analysis. These will be included in medical history summaries.

Adverse events will be categorized according to MedDRA.

6.2.3.1. Analysis Intervals

There will be up to 7 analysis intervals for safety data collected via CRF.

Table 9. Analysis Interval for AE, SAE, Medically Attended AE and Newly Diagnosed Chronic Medical Conditions

#	Analysis Interval	Analysis Population	Interval Start date (inclusive)	Interval Stop (inclusive)	Safety Data
1	Within 30 days after vaccination 1	Vax 1 Safety	Vax 1 date	Vax 1 date + 30 days	AE, SAE, MAE, NDCMC
2	Within 30 days after vaccination 2	Vax 2 Safety	Vax 2 date	Vax 2 date + 30 days	AE, SAE, MAE, NDCMC
3	Within 30 days after vaccination 3	Vax 3 Safety	Vax 3 date	Vax 3 date + 30 days	AE, SAE, MAE, NDCMC
4	Within 30 days after any vaccination	Safety	Vax 1, Vax 2, or Vax 3 date	Vax 1, Vax 2, or Vax 3 date + 30 days	AE, SAE, MAE, NDCMC
5	During the vaccination phase	Safety	Visit 1 date	Visit 6 date (or end of vaccination day)	AE, SAE, MAE, NDCMC, Days missed school due to AE
6	During the follow-up Phase	Follow-up Safety	Visit 6 date + 1 day, or end of vaccination date + 1 for early withdrawal subjects	Visit 7 date	SAE, MAE, NDCMC,
7	Throughout the study	Safety	Visit 1 date	Visit 7 date	SAE, MAE, NDCMC, Neuroinflammatory and autoimmune conditions

AE=Adverse events, SAE=Serious adverse events, MAE=Medically-attended AE, NDCMC=Newly diagnosed chronic medical conditions

6.2.3.2. Immediate Adverse Events

Any AE that occurred within the first 30 minutes after the investigational product administration will be classified as an immediate AE. Immediate AEs are a subset of AEs.

Any AE occurring on the day of vaccination will have AE onset time captured.

Four (4) analysis intervals will be applied to immediate AEs.

Table 10. Analysis Interval for Immediate AE

#	Analysis Interval	Analysis Population	Interval Start Date (inclusive)	Interval Stop (inclusive)
1	Vaccination 1	Vax 1 Safety	Vaccination 1 time	Vaccination 1 time + 30 minutes
2	Vaccination 2	Vax 2 Safety	Vaccination 2 time	Vaccination 2 time + 30 minutes
3	Vaccination 3	Vax 3 Safety	Vaccination 3 time	Vaccination 3 time + 30 minutes
4	Any vaccination	Safety	Vaccination 1, 2, or 3 time	Vaccination 1, 2, or 3 time + 30 minutes

6.2.3.3. Days of School Missed Due to AE

For each subject, the number of days of school missed because of AEs will be aggregated across the vaccination phase. Then summary statistics using mean (standard deviation), median, and range will be descriptively tabulated for the total days by each group.

The following variables will be derived:

1. Number of subjects reporting days missing school due to AE.
2. Percentage of subjects reporting days missing school due to AE among the safety population.
3. Percentage of subjects reporting days missing school due to AE among the subjects who report at least one AE during the vaccination phase.
4. Total number of days missing school due to AE during the vaccination phase.

Corresponding variables will be derived for absences from school due to related AEs only.

6.3. Other Endpoints

6.3.1. E-Diaries Completion

The following e-Diary compliance variables will be provided for each vaccination:

1. Compliance per day: the numerator is the number of subjects who completed (transmitted) the e-diary on a given day (day 1 to day 7) and the denominator is the total number of subjects who receive the vaccination.
2. At least n days: the numerator is the number of subjects who completed (transmitted) the e-diary on any n days and the denominator is the total number of subjects who received a vaccination. To be derived for $n = 1$ through 7.

6.3.2. Nonstudy Vaccination

Any *Haemophilus influenzae* type b conjugate vaccine (polyribosylribitol phosphate outer membrane protein: PRP-OMP) received prior to the signing of the ICD will be recorded in the case report form (CRF).

Any nonstudy vaccine given from the signing of the ICD to the blood draw at Visit 6 will be recorded in the CRF.

Nonstudy vaccines will be categorized according to the WHO Drug Dictionary (WHODRA).

6.3.3. Demographic, Medical History, and Baseline Characteristics Variables

The demographic variables are gender, race, ethnicity, and age (in years). Age at time of first vaccination and age at randomization will be derived based on calendar dates, ie, a subject is n years of age from their n^{th} birthday to the day before their $(n+1)^{\text{th}}$ birthday.

Medical history will be categorized according to the Medical Dictionary of Regulatory Activities (MedDRA).

Physical exam will be recorded as normal, abnormal, and not done.

6.4. Covariates

The following endpoints will further be summarized by race (White, Black, Asian and Other), by gender (Male, Female), and by country. Additionally, within each age stratum data will also be summarized by race, gender, and country:

- Proportion of subjects with hSBA titer \geq LLOQ for each of the 4 primary MnB test strains at each time point
- GMTs for each of the 4 primary MnB test strains at each time point
- Primary safety endpoints related to reactogenicity, AE, SAE, and MAE

Composite responses and 4-fold responses may additionally be summarized by age, race, gender, and country.

7. HANDLING OF MISSING VALUES

7.1. Immunogenicity Data

For the hSBA assay results, the following values will be set to missing: QNS (insufficient sera), indeterminate results, and Not Done. Subjects without a blood draw (eg, dropouts) will also have missing immunogenicity data.

The primary immunogenicity analyses will use only valid and determinate assay results with no imputation of missing values, which uses the assumption that data are missing completely at random (MCAR).¹ The approach to missing assay data depends on serology testing strategy, to be determined:

- If volume permits, subjects will have serum tested for all 4 primary strains by hSBA. In this case, descriptive summaries will explore the relationship between the missingness indicator and design variables or covariates (age, race, gender, site etc.). A sensitivity analysis using a mixed effects model with repeated measurement (MMRM) will be applied to the primary immunogenicity endpoints.

- If only 50% of subjects are tested for 2 of the 4 primary strains, and the other 50% of subjects tested for the other 2 primary strains, there will be no sensitivity analysis. Data will be assumed to be MCAR.

For the calculation of GMTs, hSBA values below LLOQ will be assigned a value of half the LLOQ. The LLOQ for CCI (A22) is 1:16, and for the other 3 primary test strains is 1:8.

